2.3.4 Secondary efficacy endpoints - Proportions

2.3.4.1 *Definition of endpoint(s)*

Secondary efficacy endpoints defined as proportions:

- Percentage of participants achieving HiSCR75 (defined as $\geq 75\%$ reduction from Baseline in the total AN count, with no increase from Baseline in abscess or draining tunnel count) at Week 16
- Percentage of participants achieving HiSCR90 (defined as $\geq 90\%$ reduction from Baseline in the total AN count, with no increase from Baseline in abscess or draining tunnel count) at Week 16
- Percentage of participants who experience improvement by at least one IHS4 stage at Week 16
- Percentage of participants achieving IHS4-55 at Week 16 (defined as achievement of a 55% reduction in IHS4 score from Baseline)
- Percentage of participants who experience a flare, defined as at least a 25% increase in AN count (with a minimum increase of 2) relative to Baseline at Week 16 (See also protocol 8.2.1.4 for definition of flare)

HiSCR75 and HiSCR90

Exploratory outcome measures that evaluated deeper clinical response included an HiSCR modification to assess the proportion of participants achieving at least 75% (HiSCR75) and 90% (HiSCR90) reduction from baseline AN count, with no increase from Baseline in abscess or draining tunnel count) at Week 16, as defined in [Table 2](#), will be analyzed.

Dichotomous IHS4

IHS4 is defined in [Section 2.3.2](#) above. Two dichotomous IHS4 scores are to be derived from the primary continuous IHS4. The first one is defined as the improvement by at least one IHS4 stage at Week 16 and the second which is also known as IHS4-55 is defined as a 55% reduction in IHS4 score from Baseline.

Disease flare

Disease flare is defined when at least a 25% increase in AN count with a minimum increase of 2 AN relative to baseline is observed. A participant's disease flare status is a dichotomous status which will be determined at each visit using these criteria and will be listed with the other lesion count assessment data in the data listings.

2.3.4.2 Main analytical approach

The estimand for proportions defined in [Table 3](#) above will be used. For the following endpoints: HiSCR75, HiSCR90 and Dichotomous IHS4; Participants with missing data at Week 16 will be imputed as non-responders. For disease flare, participants with missing data at Week 16 will be imputed as flare if a flare had occurred already before Week 16. Otherwise, no flare will be imputed. The treatment difference in response rates in SAR442970 against placebo and the corresponding 80% and 90% confidence intervals will be reported.

2.4 [REDACTED]

[REDACTED]

[REDACTED]

[REDACTED]

2.4.1 [REDACTED]

[REDACTED]

[REDACTED]

[REDACTED]

[REDACTED]

[REDACTED]

[REDACTED]

A series of horizontal black bars of varying lengths, likely representing data points or categories in a bar chart. The bars are arranged vertically and have different widths, indicating varying values or frequencies. The lengths of the bars range from approximately 10% to 100% of the total height of the chart area.

The Peak Pruritus Numerical Rating Scale

The Peak Pruritus Numerical Rating Scale (PP-NRS) is a validated single item 0-10 numeric rating scale assessing peak pruritus (itch) during the past 24 hours. The participant is asked about the severity of their pruritus with 0 = no itch and 10 = worst itch imaginable. The PP-NRS will be completed daily as a daily diary. The Week 16 average PP-NRS is calculated based on the available 7 daily assessment. Participants must have a minimum of 4 diary entries within the 7-day period prior to Week 16 to calculate the week's average. Those who don't meet this requirement will have missing data for that week.

2.4.2 [REDACTED]

[REDACTED]

[REDACTED]

[REDACTED]

[REDACTED]

[REDACTED]

2.4.3 Main analytical approach

Biologic and small molecule immunosuppressive-naïve population

Exploratory efficacy endpoints at Week 16 in the biologic and small molecule immunosuppressive-naïve population will be analyzed with the same estimand and analysis approach as the secondary efficacy endpoints defined in [Table 3](#) for the same data type (binary, continuous or skin pain), except for the following endpoint:

- Percentage of participants without analgesic use in the past 2 weeks at Weeks 16

For the percentage of participants without analgesic use in the past 2 weeks at Week 16, descriptive statistics will be provided based on data as collected i.e., without IE handling and without missing data imputation.

TNF-experienced population

Descriptive statistics will be provided for the exploratory efficacy endpoints at Week 16 in the TNF-experienced population, using the estimand defined in [Table 3](#) for binary endpoints.

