##### Participant Daily Analgesic Use Diary

*Please answer the questions below each night before you go to bed. Provide your response for each day based on the past 24 hours of that day.*

|                             | Monday   |  | Tuesday  |  | Wednesday  |  | Thursday   |  | Friday   |  | Saturday   |  | Sunday   |  |
|-----------------------------|--|--|--|--|--|--|--|--|--|--|--|--|--|--|
|                             | Did you take any Pain medication the past 24 hours? |  | Did you take any Pain medication the past 24 hours? |  | Did you take any Pain medication the past 24 hours? |  | Did you take any Pain medication the past 24 hours? |  | Did you take any Pain medication the past 24 hours? |  | Did you take any Pain medication the past 24 hours? |  | Did you take any Pain medication the past 24 hours? |  |
|                             |  Yes*                              |  No                              |
| Pain Medication             | Total dose mg  | Was the pain medication specifically for HS?             | Total dose mg  | Was the pain medication specifically for HS?             | Total dose mg  | Was the pain medication specifically for HS?             | Total dose mg  | Was the pain medication specifically for HS?             | Total dose mg  | Was the pain medication specifically for HS?             | Total dose mg  | Was the pain medication specifically for HS?             | Total dose mg  | Was the pain medication specifically for HS?             |
| Ibuprofen                   | _____ mg   |  Yes  No | _____ mg   |  Yes  No | _____ mg   |  Yes  No | _____ mg   |  Yes  No | _____ mg   |  Yes  No | _____ mg   |  Yes  No | _____ mg   |  Yes  No |

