4.4 APPENDIX 4 DATA HANDLING CONVENTIONS

Demographic formulas

- Age at onset of HS (years):
 - Year of first diagnosis of HS- Year of birth
- Time since first diagnosis of HS (years):
 - $(\text{Year of randomization} - \text{Year of first diagnosis of HS}) + (\text{Month of randomization} - \text{Month of first diagnosis of HS})/12$ if at least year and month are available
 - or
 - $(\text{Year of randomization} - \text{Year of first diagnosis of HS})$ if only year is available

Unscheduled visits

Unscheduled visit measurements of efficacy, laboratory data, vital signs, ECG and biomarkers and ADA will be used, in particular for computation of baseline, the last on-treatment value, analysis according to PCSAs, and the shift summaries for safety. They will also be included in the by-visit summaries if they are re-allocated to scheduled visits.

Biomarkers

- The baseline biomarker parameter is defined as the last non-missing value prior to the first IMP dose of IMP unless otherwise specified.
- Imputation of censored values: If any value below the lower limit of quantitation (LLOQ) is found, the values <LLOQ will be reported in tables and the associated values will be imputed by LLOQ/2 for data plotting and computation of summary statistics. If any value above the upper limit of quantitation (ULOQ) is found, the number of values >ULOQ will be reported in tables and the associated values will be imputed by the ULOQ for data plotting and computation of summary statistics. If the unit is %, the values >ULOQ will be imputed by $(100+\text{ULOQ})/2$, instead of ULOQ. Whenever possible, the value of the LLOQ and ULOQ should be displayed in plots of absolute values, whereas it is not possible when plotting percent changes from baseline. If the value of any summary statistics will be itself <LLOQ (>ULOQ, respectively), it will not be reported as such but shown as 'BLOQ' ('ALOQ', respectively).

- Change and Percent change: For biomarkers, the change and the percent change from baseline are reported in addition to the analysis values. The percent change from baseline is defined as $100 \times \frac{X-B}{B}$, with X the analysis value at a given timepoint and B the baseline analysis value for the same participant. The change from baseline is defined as $X - B$.

Analysis windows for time points

The following analysis windows will decide how the scheduled and/or unscheduled visits will be used in the by-visit analyses of efficacy, safety, PK and ADA variables.

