A measurement (scheduled or unscheduled) will be used if it is available and measurement date is within the analysis window.

After applying these time windows, if multiple assessments are associated to the same time point, the closest from the targeted study day will be used. If the difference is a tie, the value after the targeted study day will be used. If multiple valid values exist within a same day, then the first value of the day will be selected. For procedures planned on Visit 2, if it is done on the same date as the first IMP injection but the performance time is missing, it will belong to the Visit 2 window.

If there is no measurement for a given parameter in an analysis window, data will be considered missing for the corresponding visit.

Table 12 - Analysis window definition for safety analysis

Analysis visits	Targeted study day ^a	Time window				
		Vital signs	Fasting lipid panel	Non-fasting laboratory tests	Urinalysis	12-lead ECG
Period A						
Screening	-28 to -14	<-14	<-14	<-14	<-14	<-14
Baseline	1	-14 - 1	-14 - 1	-14 - 1	-14 - 1	-14 - 1
Week 2	15	2 - 21	2 - 21	2 - 21	2 - 21	2 - 21
Week 4	29	22 - 35	22 - 35	22 - 35	22 - 35	22 - 35
Week 6	43	36 - 49	36 - 49	36 - 49	36 - 49	36 - 49
Week 8	57	50 - 63	50 - 63	50 - 63	50 - 63	50 - 63
Week 10	71	64 - 77	64 - 77	64 - 77	64 - 77	64 - 77
Week 12	85	78 - 91	78 - 91	78 - 91	78 - 91	78 - 91
Week 14	99	92 - 105	92 - 105	92 - 105	92 - 105	92 - 105
Week 16	113	106 - D ^b	106 - D ^b	106 - D ^b	106 - D ^b	106 - D ^b
Period B						
Week 18	15	2 - 21	2 - 21	2 - 21	2 - 21	2 - 21
Week 20	29	22 - 35	22 - 35	22 - 35	22 - 35	22 - 35
Week 22	43	36 - 49	36 - 49	36 - 49	36 - 49	36 - 49
Week 24	57	50 - 63	50 - 63	50 - 63	50 - 63	50 - 63
Week 26	71	64 - 77	64 - 77	64 - 77	64 - 77	64 - 77
Week 28	85	78 - 112	78 - 112	78 - 112	78 - 112	78 - 112
Week 36	141	>112	>112	>112	>112	>112

a Day 1 in Period A is the day of the first blinded IMP administration (or the day of randomization for participant not exposed).

Day 1 in Period B is the day of the first open-label IMP administration.

b Last window in Period A is the 1st dose of open-label IMP administration.

Table 13 - Analysis window definition for efficacy endpoints

Analysis visit	Targeted study day ^a	Time windows			
		HS clinical parameters	Dermatology Life Quality Index	Hidradenitis Suppurativa Quality of Life	
Period A					
Screening	-28 to -14	<-14	<-14		<-14
Baseline	1	-14 - 1	-14 - 1		-14 - 1
Week 2	15	2 - 21	2 - 21		2 - 21

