Week 4	29	22 - 42	22 - 42		22 - 42
Week 6	43				
Week 8	57	43 - 70	43 - 70		43 - 70
Week 10	71				
Week 12	85	71 - 98	71 - 98		71 - 98
Week 14	99				
Week 16	113	99 - D ^b	99 - D ^b		99 - D ^b
Period B					
Week 18	15				
Week 20	29	2 - 42	2 - 42		2 - 42
Week 22	43				
Week 24	57	43 - 70	43 - 70		43 - 70
Week 26	71				
Week 28	85	>70	>70		>70

^a Day 1 in Period A is the day of the first blinded IMP administration (or the day of randomization for participant not exposed). Day 1 in Period B is the day of the first open-label IMP administration.

^b Last window in Period A is the 1st dose of open-label IMP administration.

Table 14 - Analysis window definition for daily questionnaires

Analysis visit	Targeted study day ^a	Time windows		
		Daily Diary HS-Skin Pain NRS	Daily Diary PP-NRS	Daily diary analgesic use
Period A				
Screening	-28 to -7	<-7	<-7	<-7
Baseline	1	-7 - <1	-7 - <1	-7 - <1
Week 2	15	8 - 14	8 - 14	8 - 14
Week 4	29	22 - 28	22 - 28	22 - 28
Week 6	43	36 - 42	36 - 42	36 - 42
Week 8	57	50 - 56	50 - 56	50 - 56
Week 10	71	64 - 70	64 - 70	64 - 70
Week 12	85	78 - 84	78 - 84	78 - 84
Week 14	99	92 - 98	92 - 98	92 - 98
Week 16	113	106 - D ^b	106 - D ^b	106 - D ^b
Period B				
Week 18	15	8 - 14	8 - 14	8 - 14
Week 20	29	22 - 28	22 - 28	22 - 28
Week 22	43	36 - 42	36 - 42	36 - 42
Week 24	57	50 - 56	50 - 56	50 - 56
Week 26	71	64 - 70	64 - 70	64 - 70
Week 28	85	78 - 84	78 - 84	78 - 84

a Day 1 in Period A is the day of the first blinded IMP administration (or the day of randomization for participant not exposed). Day 1 in Period B is the day of the first open-label IMP administration.

b D = minimum (Day 112, the day prior to the first open-label IMP)

Table 15 - Analysis windows for pharmacokinetics/pharmacodynamics variables

Analysis visit	Targeted study day ^a	Time windows				
		ADA	Blood biomarkers	PK	PD Biomarker	Skin Biopsy
Period A						
Screening	-28 to -14	<-14	<-14		<-14	
Baseline	1	-14 - 1	-14 - 1	≤1	-14 - 1	≤1
Week 2	15	2 - 21	2 - 21		2 - 21	
Week 4	29	22 - 42	22 - 42	2 - 49	22 - 42	
Week 6	43					
Week 8	57	43 - 70	43 - 70	50 - 63	43 - 70	
Week 10	71			64 - 77		
Week 12	85	71 - 98	71 - 98	78 - 98	71 - 98	
Week 14	99					
Week 16	113	99 - D ^b	> 1			
Period B						
Week 18	15			2 - 21		
Week 20	29	2 - 42	2 - 42	22 - 70	2 - 42	
Week 22	43					
Week 24	57	43 - 70	43 - 70		43 - 70	
Week 26	71					
Week 28	85	71 - 112	> 70	71 - 112	71 - 112	
Week 36	141	> 112		> 112	> 112	

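### SAP 2.4.3 defines an exploratory endpoint over the past 2 weeks at Week 16, but the analgesic column of SAP Table 14 gives Week 16 at most 7 diary days

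*SAP*

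**What the plan says.** SAP 2.4.3 (Main analytical approach) singles out one exploratory endpoint in the biologic and small molecule immunosuppressive-naïve population for separate handling: "Percentage of participants without analgesic use in the past 2 weeks at Weeks 16". For it, "descriptive statistics will be provided based on data as collected i.e., without IE handling and without missing data imputation".

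SAP Appendix 4 (section 4.4) sets the time windows. Its scope statement begins "The following analysis windows will decide how the scheduled and/or unscheduled visits will be used in the by-visit analyses of efficacy, safety, PK and ADA", and its rule of use is "A measurement (scheduled or unscheduled) will be used if it is available and measurement date is within the analysis window". The diary items have their own table, "Table 14 - Analysis window definition for daily questionnaires", with a column headed "Daily diary analgesic use". In that column Week 14 takes Days 92 to 98 and Week 16 takes Days 106 to D. The footnote defines the upper limit as "D = minimum (Day 112, the day prior to the first open-label IMP".

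The example diary in the protocol (Section 10.11.5) instructs participants: "Provide your response for each day based on the past 24 hours of that day". Protocol Section 6.9.2 requires analgesic use to be recorded every day through Week 28.

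**The concern.** The endpoint looks back two weeks, while the only readable window for its data covers one week or less. Each diary entry covers 24 hours, so 7 entries cannot describe 14 days. If the programmer follows Table 14, a participant whose only analgesic use fell on Days 99 to 105 is counted as having used none in the past 2 weeks. The published percentage would then carry a label that its data do not support, and the look-back would differ between participants according to visit day.

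No intercurrent-event rule or imputation applies to this endpoint, so the choice of window largely determines the reported number. What is at stake is the accuracy of one exploratory, descriptive result. Nothing in the readable text carries it into the primary or secondary analyses.

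**Working it through.** **Inputs**

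- Look-back in the endpoint definition: 2 weeks, or 14 days (SAP 2.4.3).
- Week 16 diary window: Day 106 to D, with D = min(112, first open-label day − 1) (SAP Table 14).
- Week 14 diary window: Days 92 to 98 (SAP Table 14).
- Week 16 visit: Day 113 ± 3, so Days 110 to 116 (Protocol 1.3, Schedule of Activities).
- Working assumption: the first open-label dose is given on the day of the Week 16 visit, as the schedule plans.

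**Day count**

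For a visit on day v, the 14-day look-back is Days v − 14 to v − 1. The window length is D − 106 + 1.

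| Visit day | D | Days in Week 16 window | Share of 14 | Look-back days in neither the Week 14 nor the Week 16 window |
|---|---|---|---|---|
| 110 | 109 | 4 | 29% | 99–105 |
| 111 | 110 | 5 | 36% | 99–105 |
| 112 | 111 | 6 | 43% | 99–105 |
| 113 | 112 | 7 | 50% | 99–105 |
| 114 | 112 | 7 | 50% | 100–105, 113 |
| 115 | 112 | 7 | 50% | 101–105, 113–114 |
| 116 | 112 | 7 | 50% | 102–105, 113–115 |

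The stated 14 days cannot be reproduced. Pooling the Week 14 and Week 16 windows does not help: together they cover 7 of the 14 look-back days for every visit day from 110 to 116.

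**Direction**

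In every row the Week 16 window lies inside the 14-day look-back. With complete diaries, anyone free of use over the 14 days is also free of use over the window, but the reverse need not hold. The windowed percentage therefore equals or exceeds the 14-day percentage.

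**Size, under assumed use rates**

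The documents give no rate of analgesic use, so every rate below is an assumption. With independent days and daily probability p, the analgesic-free share over k days is (1 − p)^k. For use clustered within participants I take a beta-binomial with mean m and within-participant correlation ρ. With s = (1 − ρ)/ρ, a = m·s and b = (1 − m)·s, the share is the product over i = 0, …, k − 1 of (b + i)/(a + b + i).

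| Assumption | 7 days | 14 days | Gap (points) |
|---|---|---|---|
| Independent, p = 0.01 | 93.2% | 86.9% | 6.3 |
| Independent, p = 0.05 | 69.8% | 48.8% | 21.0 |
| Independent, p = 0.10 | 47.8% | 22.9% | 24.9 |
| Mean 0.10, ρ = 0.2 | 63.5% | 51.6% | 11.9 |
| Mean 0.10, ρ = 0.5 | 76.5% | 71.6% | 4.9 |
| Mean 0.10, ρ = 0.8 | 85.3% | 83.8% | 1.5 |

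At the same mean use of 10%, the gap runs from about 25 points with independent days to under 2 points with strong clustering.

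**The case against.** The strongest objection is that the derivation may exist but be out of sight. SAP 2.4.1 and 2.4.2 are largely redacted. The one legible definition there, for peak pruritus, sets its own 7-day look-back and minimum number of entries, so that section does carry look-back rules specific to an endpoint. A 14-day rule for analgesic use could sit beside it. This stands, and it is why the conclusion is conditional. It does not remove the point, because such a rule would still disagree with the analgesic column of Table 14.

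No sentence ties this endpoint to that column. The column could instead serve by-visit summaries, or the rule on analgesic use within 5 days of Week 16 for the pain endpoints. Appendix 4 also cannot be the whole algorithm for diary data: read literally, its closest-to-target rule would keep one assessment per visit and rule out weekly averages. A programmer might therefore let the 2-week definition override the window. That is possible, but the plan does not say so, and its general rule admits data by window.

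It might be argued that analysing data as collected sets the windows aside. SAP 2.4.3 explains that phrase only as no intercurrent-event handling and no imputation, so this does not hold.

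On size, the objection is sound. Protocol 6.9.2 allows a stable ibuprofen or acetaminophen dose to continue through Week 28, which would cluster use and narrow the gap. It also allows either drug to be started after Baseline, so some gap remains possible.

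**Conclusion.** On the readable text, the endpoint definition and Table 14 disagree: 14 days against at most 7, with Days 99 to 105 in no window. If Table 14 is applied and diaries are complete, the reported analgesic-free percentage equals or exceeds the true 14-day percentage.

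A reader might infer more: that the trial will certainly report a 7-day rate under a 14-day label, and that the figure is too high in both arms by some 20 points or more. The documents do not support that. The redacted sections may hold a 14-day derivation. The inequality allows no difference at all. The large gaps arise only under independent daily use at rates that the documents do not give.

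This is a minor point about an exploratory, descriptive endpoint. The day counts for early visits assume that open-label dosing starts at the Week 16 visit.

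**What to change.** For this endpoint only, set a 14-day Week 16 window in Table 14, from Day D − 13 to Day D. D stays the earlier of Day 112 and the day before the first open-label dose, and is set to Day 112 for participants who never start open-label dosing. An on-schedule visit then uses Days 99 to 112, and a Day 110 visit uses Days 96 to 109. For visits on Days 114 to 116 the window still ends at Day 112, as the table does now. Keep the 7-day windows for the other by-visit diary summaries.

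State the minimum number of diary entries needed to classify a participant, since nothing is imputed. If the redacted text already gives a 14-day rule, refer to it from Table 14 so that the two agree.

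The readable text of SAP 2.4.3 names this endpoint at Week 16 only. If it is also reported at Week 28, the same rule is needed there: the Period B windows of Days 64 to 70 and 78 to 84 leave Days 71 to 77 unassigned.

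The alternative is to relabel the endpoint as *past 7 days*, accepting the shorter window for early visits.

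The cost is one table column or one label. The diary is already collected daily, so no new data are needed.

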2.5 EXPLORATORY EFFICACY ENDPOINT(S) ANALYSIS OF PERIOD B

The analysis of exploratory efficacy endpoints of Period B (See [Table 2](#) above) will be only descriptive. The general consideration defined in [Section 2.1](#) will be applied and no statistical testing will be implemented.

2.6 MULTIPLICITY ISSUES

No multiplicity adjustment will be applied in this proof-of-concept study.

2.7 SAFETY ANALYSES

All safety analyses will be performed for Period A and Period B separately, on the safety populations as defined in [Section 1.3](#), unless otherwise specified, using the following common rules:

- The analysis of the safety variables will be essentially descriptive, and no statistical testing is planned.
- Safety data in participants who do not belong to the safety population (e.g., exposed but not randomized) will be provided separately.

2.7.1 Extent of exposure

The extent of IMP exposure will be assessed by the duration of IMP exposure and compliance and summarized within the safety populations.

Duration of IMP exposure during Period A

Duration of IMP exposure during Period A is defined as minimum of (the first open-label IMP administration date - the first blinded IMP administration, the last blinded IMP administration date- the first blinded IMP administration date + 14 days), regardless of unplanned intermittent discontinuations.

Duration of IMP exposure during Period A will be summarized descriptively as a quantitative variable (number, mean, SD, median, minimum, and maximum). In addition, duration of treatment exposure during Period A will be summarized categorically by numbers and percentages for each of the following categories and cumulatively according to these categories:

- > 0 and ≤ 2 weeks
- > 2 and ≤ 4 weeks
- > 4 and ≤ 8 weeks
- > 8 and ≤ 12 weeks
- > 12 and ≤ 16 weeks
- > 16 weeks

Additionally, the cumulative duration of treatment exposure (expressed in participant-years) will be provided.

Duration of IMP exposure during Period B

Duration of IMP exposure during Period B is defined as the last open-label IMP administration date- the first open-label IMP administration date + 14 days, regardless of unplanned intermittent discontinuations. If the date of the last open-label dose is missing, the duration of IMP exposure will be missing.

Duration of IMP exposure during Period B will be summarized descriptively as a quantitative variable (number, mean, SD, median, minimum, and maximum). In addition, duration of treatment exposure during Period B will be summarized categorically by numbers and percentages for each of the following categories and cumulatively according to these categories:

- > 0 and ≤ 2 weeks
- > 2 and ≤ 4 weeks
- > 4 and ≤ 8 weeks
- > 8 and ≤ 12 weeks
- > 12 weeks

Additionally, the cumulative duration of treatment exposure (expressed in participant-years) will be provided.

Treatment compliance during Period A

A given administration will be considered noncompliant if the participant did not receive the number of administrations as required by the protocol. No imputation will be made for participants with missing or incomplete data.

Percentage of treatment compliance for a participant during Period A will be defined as the number of administrations that the participant was compliant divided by the total number of administrations that the participant was planned to take from the first blinded administration of IMP up to the actual last blinded administration of IMP during Period A.

Treatment compliance will be summarized quantitatively and categorically: $<80\%$, $\geq 80\%$.

Treatment compliance during Period B

A given administration will be considered noncompliant if the participant did not receive the number of administrations as required by the protocol. No imputation will be made for participants with missing or incomplete data.

Percentage of treatment compliance for a participant during Period B will be defined as the number of administrations that the participant was compliant divided by the total number of administrations that the participant was planned to take from the first open-label administration of IMP up to the actual last open-label administration of IMP during Period B.

Treatment compliance will be summarized quantitatively and categorically: $<80\%$, $\geq 80\%$.

